11.6 FOLLOW-UP VISITS

Prior to the Visit: Reminder Call

Since dry eye drops and lubricants can affect the endpoint assessments, it is important to call subjects a few days before their follow-up visits to remind them that on the day of the Follow-up visit, they should not to use any of these products before the Follow-up visit.

Order of Procedures During the Follow-Up Visit

Follow-up exams should not be performed by the clinician who performed the TearCare procedure.

A large block of text is completely redacted with black bars, representing a list of procedures or steps.

11.7 PHOTOGRAPHY DURING EXAMS AND TEARCARE PROCEDURE

Photographs or videos may be made during the baseline or follow-up exams or during the TearCare procedure. These images may be used for educational, training or

marketing purposes. Subject consent must be obtained prior to taking any photographs or videos. Subjects do not have to agree to consent to being filmed in order to participate in the study.

11.8 WITHDRAWAL AND DISCONTINUATION

All subjects have the right to withdraw at any point during the treatment without prejudice. The investigator can discontinue any subject at any time if continued participation in the study would result in harm to the subject. All efforts should be made by the investigator to retain the subject in the study. If a subject withdraws prematurely from the study, a genuine effort must be made to determine the reason(s) the subject discontinued the study. The reason must be recorded in the subject's file and on the End of Study Form.

If a subject withdraws from the study prior to receiving the TearCare, then that subject may be replaced in the study by a newly enrolled subject.

12 ADVERSE EVENTS (AEs)

Adverse Events are defined below. Adverse events that occur in the eye during the trial, whether they are considered to be device related or not, must be documented in the subject's records. Date of the event, its severity, treatment (if any) and the assessed relationship of the event to the study device will be recorded on the Adverse Event Form. Conditions which exist at the time the subject is enrolled do not need to be recorded on the Adverse Event Form as adverse events unless they increase in severity during the study.

12.1 DEFINITIONS OF AE, SAE, SADE, USADE

| | |
|-----------------------------|-------------------------------------------------------------------------------------------------------------------------------------------------------------------------------------------------------------------------------------------------------------|
| Adverse Event | Any untoward medical occurrence in a subject who has been treated with the device that does not necessarily have causal relationship with the treatment. |
| Adverse Device Effect | Any unfavorable and unintended sign (including an abnormal laboratory finding), symptom, or disease that is possibly related to the study device. |
| Serious Adverse Event (SAE) | Any untoward medical occurrence that: 
• Results in death• Is life-threatening• Requires in-patient hospitalization or prolongs existing hospitalization• Necessitates medical or |

| | |
|-------------------------------------|----------------------------------------------------------------------------------------------------------------------------------------------------------------------------------------------------------------------------------------------------------------------------------------------------------------------------------------------------------------------------------------------------------------------------------------------------------------------------------------------------------------------------------------|
| | 
surgical intervention to preclude permanent impairment of a body function or permanent damage to a body structure
 
 • Sight threatening |
| Unanticipated Adverse Device Effect | 
Any serious adverse effect on health or safety, any life-threatening problem or death caused by, or associated with a device if that effect, problem, or death was not previously identified in nature, severity, or degree of incidence in the clinical investigational plan; or any other serious problem associated with a device that relates to the rights, safety, or welfare of subjects (21 CFR 812.3(s)). Any sight-threatening event, whether listed in the protocol or not, is considered to be reportable as a UADE
 |

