This study will enroll subjects who had been previously treated with the TearCare System over one year ago as part of their participation in the TearCare arm of the TearCare pilot study. This extension of the pilot study is being conducted in order to evaluate the long-term safety and effectiveness of re-treatment with the TearCare System.

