12.3 REPORTING ADVERSE EVENTS AND UNANTICIPATED ADVERSE DEVICE EFFECTS

Identification, collection and reporting of adverse event information is the responsibility of the principal investigator. The investigator records the date of the event, its severity, treatment (if any) and the assessed relationship of the event to the study device on the Adverse Event Case Report Form (AE CRF).

All unanticipated adverse device effects (UADE) will be reported as soon as possible, but no later than 10 working days after the investigator first learns of the event, to the following two entities:

1. The study sponsor - E-mail the AE CRF to [contact]; and
2. The reviewing IRB – per the IRB's instructions.

The sponsor will conduct an evaluation of unanticipated adverse device effects. If the sponsor determines that an unanticipated adverse device effect presents an unreasonable risk to subjects, parts of the investigation presenting risks will be terminated. Termination will occur not later than 5 working days after the sponsor makes such a determination and not later than 15 working days after the sponsor first received notice of the effect.

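### The SAE definition in 12.1 covers permanent harm that needs an intervention to prevent it, but not permanent harm that actually occurs, so a lasting, non-sight-threatening eyelid or gland injury can be labelled non-serious

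*Combined protocol and SAP*

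**What the plan says.** Section 12.1 defines an SAE as an untoward medical occurrence that meets any of five bullets:

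1. "Results in death"
2. "Is life-threatening"
3. "Requires in-patient hospitalization or prolongs existing hospitalization"
4. "Necessitates medical or" "surgical intervention to preclude permanent impairment of a body function or permanent damage to a body structure" (one bullet, split by a page break)
5. "Sight threatening"

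The same table defines a UADE. That definition speaks of a serious effect, a life-threatening problem or a death that the plan did not previously identify. It then adds a residual limb for other serious device-associated problems that bear on subjects. Any sight-threatening event is also reportable as a UADE.

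Section 12.3 gives the only reporting deadline for adverse events in the visible text, and gives it for UADEs: "All unanticipated adverse device effects (UADE) will be reported as soon as possible, but no later than 10 working days". Section 20.3.4 repeats it.

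Section 12 requires adverse events in the eye to be documented whether or not they are device related, with date, severity, treatment and relationship to the device. Section 8.2 names device-related adverse events as a safety endpoint. Section 5 gives the purpose of the extension as to "evaluate the long-term safety and effectiveness of re-treatment with the TearCare System".

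**The concern.** The definition has an inverted logic. An injury that would have become permanent but was averted by treatment is serious. The same injury, if it does become permanent without such treatment, need not be.

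This matters here because the study asks about the long-term safety of treating the same eyelids again. The procedure heats the lids and then expresses the glands of all four lids by hand (Sections 6.5 and 13.6). Section 13.6 names lid overheating and abrasion of the lid surface among the main risks. Neither has to threaten sight, so the sight-threatening bullet does not reliably catch a lasting consequence. Section 13.7 describes the risks as mostly temporary and reversible, and a seriousness definition without a criterion for permanent outcome is poorly suited to flagging an exception.

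Two things are at stake: how an event is labelled when safety is summarised, and whether the investigator recognises it as belonging under the UADE reporting rule.

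**Working it through.** No arithmetic applies, and the plan has no figure of its own to reproduce. The check is to read the definition against one test case and then look for other text that closes the gap.

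**Step 1: is the wording complete?** The fourth bullet breaks across a page. Its two halves join into one grammatical sentence, and the table shows no redaction mark. Permanent damage is the object of the verb *preclude*. Read as a separate criterion, it would not follow on from the lead-in to the list. The omission is therefore in the definition and is not an effect of the text extraction.

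**Step 2: the test case.** Take a permanent eyelid or gland injury that is not fatal or life-threatening, leaves sight unaffected, leads to no hospital stay, and neither needed nor received an intervention to prevent permanence. The example is mine. The visible plan does not list such an event.

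| SAE criterion (12.1) | Met by the test case? |
|---|---|
| Death | No |
| Life-threatening | No |
| Hospitalization, new or prolonged | No |
| Intervention needed to avert permanent harm | No |
| Threat to sight | No |

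Result: 0 of 5 criteria. With a criterion for resulting permanent harm added, the case would meet 1 of 6.

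**Step 3: does other text make the event serious?**

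- *Sections 12 and 12.3* ensure that it is recorded, with severity and relationship. They do not assign seriousness. The recording fields they name do not include outcome or permanence. The form itself is not in the text, so it may hold more.
- *Section 8.2* counts it as a device-related adverse event if it is judged related. It is counted there whatever its seriousness.
- *The UADE definition in 12.1* uses *serious* in its first and residual limbs without tying the word to the SAE bullets. An investigator could report the event there. However, the SAE bullets are the only visible definition of *serious*, and they do not direct the investigator to do so.
- *Section 12.2*, the list of anticipated events, appears in the table of contents but not in the text available. I draw nothing from its absence. Its content does matter, because the first UADE limb applies only to effects the plan had not identified.

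**Step 4: the reporting consequence.** The 10-working-day report can be missed only if all of these hold: the event is device-associated, it is unanticipated, and the investigator follows the SAE bullets in deciding that it is not serious.

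**The case against.** The strongest reply is that little is lost in practice. Ocular adverse events are recorded whatever their seriousness, and related ones count under a stated safety endpoint. The sponsor reviews or collects the case report forms periodically (Section 15.1). Section 13.6 provides for a full eye exam at each visit, and Section 24.1 includes the lid margins in the eye exam. The gap is also narrow: medical intervention is a broad term, so many lid injuries would meet the fourth bullet. The previous pilot reported no adverse events (Section 7.2). All of this stands. It limits the consequence but does not supply the missing criterion.

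A reader might infer two stronger conclusions, and the documents support neither.

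- *That the gap removes the 10-working-day report.* It does not do so of itself. The residual UADE limb is not confined to the five SAE bullets, so the event can be reported as the text stands. The unseen Section 12.2 may also settle whether such an injury counts as anticipated. The supportable statement is that the report may be missed.
- *That one misclassified subject among 12 would move a reported SAE rate from 1/12 to 0/12.* No SAE rate appears among the visible endpoints, and some items in Section 8.2 are redacted. Section 14.4 plans descriptive statistics only, with no hypothesis and no pass/fail criterion (Sections 14.1 and 14.3). The shift also presumes that an event of exactly this type occurs. It is an illustration and says nothing about the size of the problem.

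**Conclusion.** The point holds as a defect in a stated classification rule. The SAE definition has no criterion for permanent impairment or damage that actually results, and no visible text corrects this. The effect is on the label *serious* and, conditionally, on prompt UADE reporting. It is not that lasting harm would go unrecorded.

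No numerical size is attached. The finding is that a plausible class of event meets none of the five criteria. It rests on three assumptions: the table in 12.1 is complete as shown, eyelid and gland injuries are treated as events in the eye for Section 12, and the unseen Section 12.2 contains no seriousness rule of its own.

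The change is worth making because long-term safety is part of the study objective. Adverse event identification rests with the principal investigator (Section 12.3), in a single-center study conducted by a co-inventor of the device (Section 6.4) with no specific steps against bias (Section 9). An explicit criterion leaves less to individual judgement.

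**What to change.** - Add one generic bullet to the SAE definition in 12.1 for an event that *results in* permanent impairment of function or permanent structural damage, with the same body-function and body-structure terms as the existing fourth bullet.
- Keep the existing fourth bullet.
- State in 12.1 that *serious* in the UADE definition includes the new criterion.
- Use identical wording on the adverse event CRF.

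Do not name the meibomian glands in the bullet. Gland secretion is scored as an effectiveness endpoint (Sections 8.1 and 24.2), and naming the glands would invite dispute over whether a fall in the number of secreting glands is permanent damage or lack of effect.

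The cost is one new SAE bullet, a clarifying sentence in the UADE definition, matching text on the form, and an occasional extra event classed as serious. No treatment, visit or measurement changes.

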12.3 REPORTING ADVERSE EVENTS AND UNANTICIPATED ADVERSE DEVICE EFFECTS

Identification, collection and reporting of adverse event information is the responsibility of the principal investigator. The investigator records the date of the event, its severity, treatment (if any) and the assessed relationship of the event to the study device on the Adverse Event Case Report Form (AE CRF).

All unanticipated adverse device effects (UADE) will be reported as soon as possible, but no later than 10 working days after the investigator first learns of the event, to the following two entities:

1. The study sponsor - E-mail the AE CRF to [contact]; and
2. The reviewing IRB – per the IRB's instructions.

The sponsor will conduct an evaluation of unanticipated adverse device effects. If the sponsor determines that an unanticipated adverse device effect presents an unreasonable risk to subjects, parts of the investigation presenting risks will be terminated. Termination will occur not later than 5 working days after the sponsor makes such a determination and not later than 15 working days after the sponsor first received notice of the effect.

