6.3 INSTRUCTIONS FOR USE

Instructions for Use are provided with each TearCare System.

6.4 SUMMARY OF THE TRAINING AND EXPERIENCE NEEDED FOR USE OF DEVICE UNDER INVESTIGATION

This is a single-center study, conducted by [name]. [name] is a co-inventor of the TearCare System and is familiar with its proper use. He will review the Instructions for Use in advance of initiating the investigation.

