6.5 DESCRIPTION OF ASSOCIATED MEDICAL OR SURGICAL PROCEDURES

Within 10 minutes following the 15-minute TearCare session, the investigator will perform manual Meibomian gland expression of all 4 eyelids under topical anesthesia with ophthalmic tetracaine 0.5% drops.

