9 STUDY DESIGN

This is a prospective, non-randomized, single-center case series study. No specific attempts will be made for minimization of bias, such as blinding or masking.

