22 PUBLICATION POLICY

[name], the Principal Investigator, may publish the data in a medical newsletter or ophthalmic journal.

[REDACTED]

24 APPENDIX A – METHODS FOR OCULAR EXAMS AND TESTS AND ADMINISTRATION OF QUESTIONNAIRES

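### The visible plan does not give the separate follow-up examiner the first judgment on adverse events and device relationship; Section 12.3 places it with the principal investigator, who appears to be the treating co-inventor

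*Combined protocol and SAP*

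**What the plan says.** Section 12.3 puts adverse events in one person's charge: "Identification, collection and reporting of adverse event information is the responsibility of the principal investigator". It continues: "The investigator records the date of the event, its severity, treatment (if any) and the assessed relationship of the event to the study device".

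Other sections indicate who that person is. Section 6.4 says that the person conducting this single-center study "is a co-inventor of the TearCare System and is familiar with its proper use". Section 22 names one individual as "the Principal Investigator, may publish the data in a medical newsletter or ophthalmic journal". Under Section 6.5, after the heating session, "the investigator will perform manual Meibomian gland expression of all 4 eyelids". Section 13.6 adds that every treatment takes place under the investigator's direct supervision and that the supervising physician places the heating devices on the lids.

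Section 11.6 separates treatment from later examination: "Follow-up exams should not be performed by the clinician who performed the TearCare procedure". The rest of that section, which sets out the order of procedures at the visit, is blacked out.

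Section 8.2 lists device-related adverse events and best spectacle-corrected acuity as safety endpoints, with other entries blacked out. Section 12 requires every ocular event to be documented, related or not. It exempts conditions present at enrollment unless they become more severe.

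**The concern.** The plan has a non-treating clinician at each follow-up visit, but the visible text gives that clinician no stated part in the adverse-event record. Section 12.3 leaves three judgments with the principal investigator or the investigator: whether something is an event, how severe it is, and whether the device caused it. The person making them very probably gave the treatment and has an interest in the device.

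Two of these judgments carry particular weight here. The listed endpoint counts only device-related events, so the relationship call decides what enters it. Severity matters because every subject enters with symptomatic dry eye (SPEED score of at least 6, Section 10.1) and Section 13.6 names worsening dry eye symptoms as a major risk. Under the Section 12 exemption, worsening becomes an event only if someone judges that severity has increased.

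At stake is how a low or zero count can be read. The earlier pilot reported no adverse events in either group (Section 7.2). A second low count, in at most 12 subjects with no control arm, is informative only to the extent that recording is complete and grading is even-handed.

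**Working it through.** The documents give no figure to reproduce. Section 14.2 takes the 12 subjects from the size of the pilot's TearCare arm, and Section 14.1 states no hypothesis. The check is first a comparison of the sections, then an illustration of size.

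**Who does what**

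| Task | Who, in the visible text | Section |
|---|---|---|
| Conducts the study | A co-inventor of the device | 6.4 |
| Gland expression | The investigator | 6.5 |
| Applies the devices and supervises treatment | Supervising physician; the investigator | 13.6 |
| Follow-up exams | Not the clinician who performed the procedure | 11.6 |
| Identifying, collecting and reporting events | Principal investigator | 12.3 |
| Recording severity and device relationship | The investigator | 12.3 |
| Second look at events | Sponsor, for unanticipated adverse device effects only | 12.3 |

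That the principal investigator, the treating clinician and the co-inventor are one person is an inference. It rests on one center, one named Principal Investigator and a study conducted by the co-inventor. Section 15.1 allows for more than one investigator.

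The other safeguards do not fill the gap. Documenting all ocular events helps only once someone has decided that an event occurred. The sponsor's evaluation does not reach ordinary cases of discomfort, blurred vision or lid inflammation, which Section 13.4 already names. Section 15.2 makes the case report form its own source document, so if that form is the only record, a monitor has nothing separate to compare it with.

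**Illustration of size**

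Inputs: n = 12 (Section 11.2). The true per-subject risk p and the share s of affected subjects who are recorded are assumptions, because the documents give neither.

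Chance of reporting zero affected subjects = (1 − p·s)^12.

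| p | s = 1 | s = 0.75 | s = 0.5 |
|---|---|---|---|
| 5% | 0.95^12 = 54.0% | 63.2% | 73.8% |
| 10% | 0.90^12 = 28.2% | 0.925^12 = 39.2% | 0.95^12 = 54.0% |
| 20% | 0.80^12 = 6.9% | 0.85^12 = 14.2% | 0.90^12 = 28.2% |

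Exact two-sided 95% intervals:
- 0/12: upper limit 1 − 0.025^(1/12) = 26.5%, so 0 to 26.5%.
- 1/12: lower limit 1 − 0.975^(1/12) = 0.2%. The upper limit solves (1 − p)^12 + 12p(1 − p)^11 = 0.025, which gives 38.5%.

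One affected subject left unrecorded therefore changes the reported upper limit from 38.5% to 26.5%. The lower figure is valid only if recording was complete.

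**The case against.** The strongest reply has five parts.

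1. **Section 11.6 is not confined to effectiveness.** It covers follow-up exams in general. Those plausibly include acuity (Section 24.5), the slit-lamp examination for redness, discharge and lid changes (Section 24.1) and staining (Section 24.4). A reader might infer that effectiveness is protected and safety is not. The documents do not support that, because objective safety signs at follow-up are probably read by the non-treating clinician. What remains open is reported symptoms and the judgments of severity and relationship.

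2. **Responsibility is not sole detection.** Making the principal investigator responsible for adverse events is a usual allocation. It does not stop the examiner or site staff from noticing events and passing them on. A reader might infer that the principal investigator personally finds and grades every event, but Section 12.3 does not go that far. This part stands. The point is only that nobody else is visibly assigned the first judgment.

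3. **Relevant text is hidden.** The follow-up procedures in 11.6 are redacted, and Sections 11.1, 11.5.3 and 12.2 and Table 2 are not in the public copy. An adverse-event step for the examiner cannot be excluded. This stands as a limit.

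4. **The recording shares are assumed.** They would apply to any cause of under-recording and are not tied to who records. At 10% risk, full recording already yields zero events 28% of the time, so small numbers alone explain much of the uncertainty. This also stands.

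5. **The study is modest and open about its limits.** Section 9 says: "No specific attempts will be made for minimization of bias, such as blinding or masking". Sections 14.3 and 14.4 set no pass/fail criteria and plan descriptive statistics only. That limits the consequences. It is not a reason to leave out a step that needs no extra staff, since safety is part of the stated objective (Section 4) and analysis cannot recover an event that was never recorded.

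**Conclusion.** The concern holds as a gap in who makes the first judgment. In the visible text, Section 12.3 leaves the identification, severity and device relationship of events with the principal investigator or the investigator. By strong inference that is the treating co-inventor. The independent examiner already required by 11.6 is not given the first record. The change is worth making because it bears on a listed safety endpoint and costs little.

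A reader might infer that harms are, or were, under-recorded, or that the pilot's zero count is a sign of it. Nothing in the documents shows either.

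The size is illustrative. With assumed true risks of 10% and 20%, recording half instead of all affected subjects raises the chance of a zero count from 28% to 54% and from 7% to 28%. With three-quarters recorded, the figures are 39% and 14%. The conclusion rests on the inferred identity of the principal investigator and on the redacted part of 11.6 not already assigning this task to the examiner.

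**What to change.** Add to Section 12.3 text along these lines:

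> At each follow-up visit, the clinician who performs the exam under Section 11.6 asks the subject a standard question about events since the last visit. That clinician records each event's date, severity and relationship to the device on the Adverse Event Form before the principal investigator reviews it. The principal investigator remains responsible for reporting and may add events or a separate assessment. Both assessments are kept.

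Add to Section 14.4 that the report lists all ocular adverse events regardless of relationship, alongside the device-related count, and identifies treatment-day events as recorded by the treating investigator. That label is needed because the first follow-up visit is at 1 month. The examiner cannot observe events on the day of treatment and would have only the subject's recall of them.

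If the redacted part of 11.6 already gives the examiner this task, a cross-reference in 12.3 covers the first part, provided that the task includes severity and device relationship.

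The cost is the wording, a place on the form for two assessments, and a few minutes per visit from an examiner the plan already requires. The event count may come out slightly less favourable. The examiner remains an unmasked clinician at a single-center study, so the change reduces the risk of bias without removing it, and the gain cannot be quantified from the documents.
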